**11.13.4. Sub-study Amendment Design**

The A2M sub-study will consist of three phases including a Screening Phase (1 injection interval: 4 weeks for Q4W subjects and 8 weeks for Q8W subjects), a Thigh Injection Phase 16 weeks of thigh injections, 4 injection intervals for Q4W and 2 injection intervals for Q8W) and a Return to Gluteal Injection Phase (8 weeks of gluteal injections for both Q4W subjects and Q8W subjects). At the conclusion of the sub-study, participants will have the option to continue on the A2M main study or if commercial access treatment is available, the participant can transition off the sub-study and withdraw from A2M and proceed directly to CAB/RPV LA.

**Figure 21 Thigh Sub-study Amendment Design**

**NOTE:** All injection visits during the sub-study should kept to the same projected visit schedule as in the parent study.

**11.13.4.1. Sub-study Amendment: Inclusion and Exclusion Criteria**

**11.13.4.1.1. Sub-study Inclusion Criteria**

1. Capable of giving signed informed consent (Sub-study specific informed consent), which includes compliance with the requirements and restrictions listed in the consent form and in this protocol. Eligible participants or their legal guardians (and next of kin when locally required), must sign a written Informed Consent Form before any protocol-specified assessments are conducted. Enrolment of participants who are unable to provide direct informed consent is optional and will be based on local legal/regulatory requirements and site feasibility to conduct protocol procedures.
2. Eligible participants must have been on CAB LA + RPV LA regimen for a minimum of 152 weeks while on the ATLAS2-M study. Any disruptions in dosing during ATLAS2-M must be discussed with the Medical Monitor for a final determination of eligibility into the sub-study.
3. Plasma HIV-1 RNA <50 c/mL at Sub-Study Screening.

**11.13.4.1.2. Sub-study Exclusion Criteria**

4. More than 1 plasma HIV-1 RNA measurement  $\geq 50$  c/mL to <200 c/mL (virologic blip) within 24 weeks prior to sub-study Screening visit.

5. Any Suspected Virologic Failure (HIV-RNA>200 c/mL) as defined in Section [5.5.5.2](#) during ATLAS-2M study.
6. Subjects planning to require oral bridging during participation in the ATLAS-2M sub-study.
7. The participant has a tattoo or any dermatological condition overlying the thigh region which may interfere with interpretation of injection site reactions.
8. Any condition which, in the opinion of the Investigator, may interfere with the absorption, distribution, metabolism or excretion of the study drugs or render the participant unable to receive study medication.

Additionally, the following entry criteria detailed for the ATLAS-2M main study apply to the sub-study as well :

#### A2M parent study - Inclusion criteria

9. A female participant is eligible to participate if she is not pregnant (as confirmed by a negative serum human chorionic gonadotropin (hCG) test) not lactating, and at least one of the following conditions applies:
  - a. *Non-reproductive* potential defined as:
    - Pre-menopausal females with one of the following:
      - Documented tubal ligation
      - Documented hysteroscopic tubal occlusion procedure with follow-up confirmation of bilateral tubal occlusion
      - Hysterectomy
      - Documented Bilateral Oophorectomy
    - Postmenopausal defined as 12 months of spontaneous amenorrhea [in questionable cases a blood sample with simultaneous follicle stimulating hormone (FSH) and estradiol levels consistent with menopause (refer to laboratory reference ranges for confirmatory levels)]. Females on hormone replacement therapy (HRT) and whose menopausal status is in doubt will be required to use one of the highly effective contraception methods if they wish to continue their HRT during the study. Otherwise, they must discontinue HRT to allow confirmation of post-menopausal status prior to study enrolment.
  - b. **Reproductive potential** and agrees to follow one of the options listed in the Modified List of Highly Effective Methods for Avoiding Pregnancy in Females of Reproductive Potential (FRP) from 30 days prior to the first dose of study medication, throughout the study, for at least 30 days after discontinuation of all

oral study medications, and for at least 52 weeks after discontinuation of CAB LA and RPV LA.

The investigator is responsible for ensuring that participants understand how to properly use these methods of contraception.

#### **A2M parent study - Exclusionary medical conditions- for all participants**

10. Women who are pregnant, breastfeeding or plan to become pregnant or breastfeed during the study
11. Any evidence of a current Center for Disease Control and Prevention (CDC) Stage 3 disease [CDC, 2014] , except cutaneous Kaposi's sarcoma not requiring systemic therapy, and CD4+ counts <200 cells/ $\mu$ L are not exclusionary.
12. Participants with moderate to severe hepatic impairment.
13. Any pre-existing physical or mental condition (including substance use disorder) which, in the opinion of the Investigator, may interfere with the participant's ability to comply with the dosing schedule and/or protocol evaluations or which may compromise the safety of the participant.
14. Participants determined by the Investigator to have a high risk of seizures, including participants with an unstable or poorly controlled seizure disorder. A participant with a prior history of seizure may be considered for enrolment if the Investigator believes the risk of seizure recurrence is low. All cases of prior seizure history should be discussed with the Medical Monitor prior to enrolment.
15. Participants who, in the investigator's judgment, pose a significant suicide risk. Participant's recent history of suicidal behavior and/or suicidal ideation should be considered when evaluating for suicide risk.
16. Unstable liver disease (as defined by any of the following: presence of ascites, encephalopathy, coagulopathy, hypoalbuminemia, esophageal or gastric varices, or persistent jaundice or cirrhosis), known biliary abnormalities (with the exception of Gilbert's syndrome or asymptomatic gallstones or otherwise stable chronic liver disease per investigator assessment).
17. History of liver cirrhosis with or without hepatitis viral co-infection.
18. Ongoing or clinically relevant pancreatitis.
19. Clinically significant cardiovascular disease, as defined by history/evidence of congestive heart failure, symptomatic arrhythmia, angina/ischemia, coronary artery bypass grafting (CABG) surgery or percutaneous transluminal coronary angioplasty (PTCA) or any clinically significant cardiac disease.
20. Ongoing malignancy other than cutaneous Kaposi's sarcoma, basal cell carcinoma, or resected, non-invasive cutaneous squamous cell carcinoma, or cervical intraepithelial neoplasia; other localized malignancies require agreement between the investigator and the Study medical monitor for inclusion of the participant prior to randomization.
21. Any condition which, in the opinion of the Investigator, may interfere with the

absorption, distribution, metabolism or excretion of the study drugs or render the participant unable to receive study medication.
 
22. History or presence of allergy or intolerance to the study drugs or their components or drugs of their class. In addition, if heparin is used during PK sampling, participants with a history of sensitivity to heparin or heparin-induced thrombocytopenia must not be enrolled.
 
23. Current or anticipated need for chronic anti-coagulation with the exception of the use of low dose acetylsalicylic acid (<math>\leq 325</math> mg) or hereditary coagulation and platelet disorders such as haemophilia or Von Willebrand Disease.

A2M parent study - Exclusionary Laboratory Values or Clinical Assessments at Screening (a single repeat to determine eligibility is allowed)

24. Any verified Grade 4 laboratory abnormality. A single repeat test is allowed during the Screening phase to verify a result.
 
25. Any acute laboratory abnormality at Screening, which, in the opinion of the investigator, would preclude the participant's participation in the study of an investigational compound.
 
26. Participant has estimated creatine clearance <math>< 50</math> mL/min per <math>1.73\text{m}^2</math> via Chronic Kidney Disease-Epidemiology Collaboration (CKD-EPI) Method.
 
27. Alanine aminotransferase (ALT) <math>\geq 3 \times</math> ULN at Screening.

### A2M parent study - Concomitant Medications

28. Exposure to an experimental drug (with the exception of those in the ATLAS-2M study including CAB, CAB LA, and RPV, RPV LA) or experimental vaccine within either 30 days, 5 half-lives of the test agent, or twice the duration of the biological effect of the test agent, whichever is longer, prior to Day 1 of this study;
29. Treatment with any of the following agents within 28 days of Screening:
  - radiation therapy;
  - cytotoxic chemotherapeutic agents;
  - tuberculosis therapy with the exception of isoniazid (isonicotinylhydrazid, INH);
  - anti-coagulation agents;
  - Immunomodulators that alter immune responses such as chronic systemic corticosteroids, interleukins, or interferons. Note: Participants using short-term (e.g.  $\leq 21$  days) systemic corticosteroid treatment; topical, inhaled and intranasal corticosteroids are eligible for enrolment.
30. Treatment with an HIV-1 immunotherapeutic vaccine within 90 days of Screening.
31. Use of medications which are associated with Torsade de Pointes. (See SPM for a list of relevant medications).
32. Participants receiving any prohibited medication and who are unwilling or unable to switch to an alternate medication. Note: Any prohibited medications that decrease CAB or RPV concentrations should be discontinued for a minimum of four weeks or a minimum of three half-lives (whichever is longer) prior to the first dose and any other prohibited medications should be discontinued for a minimum of two weeks or a minimum of three half-lives (whichever is longer) prior to the first dose.

#### 11.13.4.2. Screening Phase (Gluteal IM)

Eligibility criteria must be assessed at the Screening visit and confirmed visit prior to the first Thigh injection. Participants who are enrolled in the sub-study and subsequently withdrawn from the main A2M study for any reason may not be re-screened. Screening procedures should occur within 35 days prior to Day 1 for Q4W subjects and 63 days prior to Day 1 for Q8W subjects of the first dose in the Thigh Injection Phase.

After the Screening visit, participants will need to return to the clinic 1 week later (for Q4W subjects) and 1 week and 4 weeks later (for Q8W subjects) to obtain PK sampling as outlined in the [Sub-study Time and Event Table](#).

#### 11.13.4.3. Thigh injections Phase (16 weeks)

**For participants receiving monthly (Q4W) IM injections while on A2M**

After confirming eligibility into the sub-study, participants will enter into the Thigh Injection Phase and receive an intramuscular injection of CAB LA (2 mL; 400 mg) on one lateral thigh and RPV LA (2 mL; 600 mg) into the opposite lateral thigh at the following visits ( $\pm 7$  days):

- Day 1
- Week 4
- Week 8
- Week 12

Participants will remain in the research unit for at least 2 hours after the injection for post-dose PK sampling and safety assessments.

After certain visits, participants will need to return to the clinic 1 week after the injection for PK sampling as outlined in Time and Event Table Section [11.13.5.1](#).

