Injection Site Pruritus	Itching localized to the injection site that is relieved spontaneously or in < 48 hours of treatment	Itching beyond the injection site that is not generalized OR Itching localized to the injection site requiring ≥ 48 hours treatment	Generalized itching causing inability to perform usual social & functional activities	NA

 Injection Site Erythema or Redness should be evaluated and graded using the greatest single diameter or measured surface area.

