#### **For participants receiving 2M (Q8W) IM injections while on ATLAS 2M:**

After confirming eligibility into the sub-study, participants will enter into the Thigh Injection Phase and receive an intramuscular injection of CAB LA (3 mL; 600 mg) on one lateral thigh and RPV LA (3 mL; 900 mg) into the opposite lateral thigh at the following visits:

- Day 1
- Week 8

Participants will remain in the research unit for at least 2 hours after the injection for post-dose PK sampling and safety assessments.

Participants will then return to the clinic 1 week and 4 weeks after the injection for PK sampling as outlined in Time and Event Table Section [11.13.5.2](#).

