**11.13.5. Sub-study: Time and Events table**

**11.13.5.1. Sub-study: Time and Events Table for CAB LA + RPV LA Q4 Weekly Administration**

Procedure	Screening Phase d Gluteal administration		Thigh Injection Phase d Q4 Weekly thigh administration						Return to Gluteal Injection Phase d Q4 Weekly gluteal admin.			
	Screening (Week -4)	Week -3	Day1	Week 1	Week 4	Week 8	Week 12	Week 13	Week 16	Week 17	Week 20	Week 24
IM treatment administration i	X		X		X	X	X		X		X	
Written Inform consent	X											
Eligibility Verification (Inclusion/Exclusion criteria)	X											
Symptom directed physical exam and Medical assessment a	X		X		X	X	X		X		X	X
Weight and BMI			X						X			

Procedure	Screening Phase d Gluteal administration		Thigh Injection Phase d Q4 Weekly thigh administration						Return to Gluteal Injection Phase d Q4 Weekly gluteal admin.			
	Screening (Week -4)	Week -3	Day1	Week 1	Week 4	Week 8	Week 12	Week 13	Week 16	Week 17	Week 20	Week 24
Vital Signs, BP, HR, temp b	X		X						X			
Smoking status	X											
12-lead ECG c	X		X						X			
HIV associated conditions	X	X	X	X	X	X	X	X	X	X	X	X
AEs, SAEs, concomitant medications	X	X	X	X	X	X	X	X	X	X	X	X
ISR assessments for IM injections	X	X	X	X	X	X	X	X	X	X	X	X
Clinical Chemistry and Hematology	X		X		X	X	X		X			X
Pregnancy Testing, SERUM c	S		S		S	S	S		S		U	S

Procedure	Screening Phase d Gluteal administration		Thigh Injection Phase d Q4 Weekly thigh administration						Return to Gluteal Injection Phase d Q4 Weekly gluteal admin.			
	Screening (Week -4)	Week -3	Day1	Week 1	Week 4	Week 8	Week 12	Week 13	Week 16	Week 17	Week 20	Week 24
HIV-1 RNA and sample for storage (S)	X		X		X	X	X		X			X
CD4+ cell count	X		X		X	X	X		X			X
CD8+ cell count			X						X			
Urinalysis f			X						X			
Fasting lab assessments: Glucose, Cholesterol (Total, HDL and LDL) and triglycerides g			X						X			
PBMC for storage			X									

Procedure	Screening Phase d Gluteal administration		Thigh Injection Phase d Q4 Weekly thigh administration						Return to Gluteal Injection Phase d Q4 Weekly gluteal admin.			
	Screening (Week -4)	Week -3	Day1	Week 1	Week 4	Week 8	Week 12	Week 13	Week 16	Week 17	Week 20	Week 24

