#### **Preference Questionnaire**

A preference question was used to assess patients’ preference, and reasons for preference, for the thigh injections compared with the gluteal injections. The “Preference” questionnaire will include a single item questions evaluating preference of HIV treatment and the attributes supporting this preference.

**11.13.5.4. Sub-study: Pharmacokinetics sample collection****Table 14 Sub-study CAB and RPV Plasma Pharmacokinetic Sample Schedule**

Group	Analytes	Sample Times Relative to Dose
Participants receiving CAB LA + RPV LA Q4W injections	CAB and RPV	Pre-Dose: Screening (Week -4), Day 1, Week 4, Week 8, Week 12, Week 16 2 hours Post dose: Day 1, Week 4, Week 8, Week 12 1 Week Post dose: Week -3, Week 1, Week 13
Participants receiving CAB LA + RPV LA Q8W injections	CAB and RPV	Pre-Dose: Screening (Week -8), Day 1, Week 8, Week 16 2 hours Post dose: Day 1, Week 8 1 Week Post dose: Week -7, Week 1, Week 9 4 Week Post dose: Week -4, Week 4, Week 12

**PK window collection:** All scheduled PK samples should be collected on the Day of the corresponding visit. Pre-dose samples will be taken prior to performing dosing within the clinic.

Additional details concerning handling of PK samples, labeling and shipping directions will be supplied in the central laboratory manual.

**11.13.6. Sub-study Amendment: Study Treatment****11.13.6.1. Sub-study Amendment: Investigational Product and Other Study treatment**

Please refer to Sections [6.1.1.3](#) Cabotegravir Injectable Suspension (CAB LA) and Section [6.1.1.4](#) Rilpivirine Injectable Suspension (RPV LA) of main A2M protocol.

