#### **11.13.6.3. Oral Bridging during the Sub-study**

Given the limited number of thigh injections for both Q4W (4 injections) and Q8W (2 injections) during the sub-study, any oral bridging will not be allowed in this sub-study.

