#### **11.13.8.4.2. Secondary and Exploratory Analyses**

The proportion of participants with HIV-1 RNA  $\geq 50$  c/mL and HIV-1 RNA  $< 50$  c/mL during the thigh injection phase will be summarized using FDA Snapshot algorithm for the ITT-E population for the substudy. Proportion of participants with protocol-defined confirmed virologic failures will also be summarized over time.

The proportion of participants reporting AEs will be tabulated for each treatment group. The following summaries of AEs will be provided:

- Incidence and severity of all AEs
- Incidence and severity of treatment related AEs
- Incidence and severity of AEs leading to withdrawal
- Incidence of SAEs
- ISR AEs from study drug injections at the event level and subject level, separately.
- Change from baseline (latest non-missing value prior to the first thigh injection) in laboratory will be summarized by visit and treatment group.
- The incidence of observed genotypic and phenotypic resistance to NRTIs and INIs, PIs, and NNRTIs will be summarized by treatment arm for subjects meeting confirmed virologic failure criteria.

The health outcomes analyses include analyses of data collected from the following four questionnaires, HIVTSQ (both s and c versions), NRS and Preference between thigh and gluteal injections. Further details will be provided in the RAP.

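### Thigh sub-study: only 2 of 4 Q4W thigh injections have a 1-week site check, against 2 of 2 in Q8W, so event-level ISR tables may under-count or under-grade Q4W thigh reactions

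*Protocol*

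**What the plan says.** The sub-study gives four thigh injections in Q4W (Day 1, Weeks 4, 8 and 12) and two in Q8W (Day 1, Week 8). Section 11.13.6.3 confirms the counts: "Given the limited number of thigh injections for both Q4W (4 injections) and Q8W (2 injections) during the sub-study".

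Return visits differ by arm. For Q4W, Section 11.13.4.3 says "After certain visits, participants will need to return to the clinic 1 week after the injection for PK sampling". For Q8W it says "Participants will then return to the clinic 1 week and 4 weeks after the injection for PK sampling". Table 14 lists the 1-week samples as "Week -3, Week 1, Week 13" for Q4W and "Week -7, Week 1, Week 9" for Q8W. The Time and Events tables (11.13.5.1 and 11.13.5.2) mark the row "ISR assessments for IM injections" at every visit column in both arms. They add a Week 17 visit, one week after the Week 16 gluteal injection, in both arms.

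In the thigh phase, participants in both arms stay on site for at least 2 hours after each injection for PK sampling and safety assessments.

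Section 11.13.3 makes ISR incidence and severity during the thigh phase a secondary endpoint. Section 11.13.8.4.2 tabulates adverse events by treatment group and includes "ISR AEs from study drug injections at the event level and subject level, separately". It makes no allowance for the different visit patterns.

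**The concern.** An event-level table treats each injection as an equal opportunity to observe a reaction, and here the opportunity is not equal. After the Q4W Week 4 and Week 8 injections the next scheduled contact is the following injection visit, 4 weeks later. Section 11.13.1 describes thigh ISRs in the Phase 1 study as of limited duration, and Section 7.4.5.10 treats persistence beyond 2 weeks as a matter for the Medical Monitor. Many reactions would therefore be gone by 4 weeks. Size-based grading needs a visible lesion. Footnote 12 of the grading table in Appendix 2 says "Injection Site Erythema or Redness should be evaluated and graded using the greatest single diameter or measured surface area", and induration is graded on the same scale.

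The pain scale has the same gap. The Q4W table marks the NRS at Day 1, Week 1, Week 12 and Week 13, and leaves Weeks 4 and 8 blank. In Q8W the NRS is taken on the day of, and one week after, both thigh injections.

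Two readings of the ISR table are exposed: Q4W against Q8W per injection, and thigh against gluteal within Q4W, where the Screening injection does have a 1-week check. Section 11.13.2 says the sub-study is meant to support home administration by showing similar tolerability at the two sites. Missed thigh reactions would push toward that conclusion. The ISR tables are descriptive, with no test behind them, so how evenly reactions were looked for decides what they can show.

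**Working it through.** **Nearest stated figure.** The protocol states no ISR capture rate. The closest safety figures, in Section 11.13.8.2, reproduce. At a true rate of 0.5% and n=41, the chance of at least one event is 1 − 0.995^41 = 18.6% (18.2% at n=40, as in Table 17), against about 18% stated. The one-sided 95% upper limit for 0/41 is 1 − 0.05^(1/41) = 7.05%, against 7.0% stated. Neither figure bears on ascertainment.

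**Visit count** (from Sections 11.13.4.3, 11.13.5.1, 11.13.5.2 and Table 14):

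| Injection | Arm | 1-week visit | First scheduled check after injection day | NRS on the day and at 1 week |
|---|---|---|---|---|
| Gluteal, Screening | Q4W | Week -3 | 1 week | yes |
| Thigh, Day 1 | Q4W | Week 1 | 1 week | yes |
| Thigh, Week 4 | Q4W | none | 4 weeks | neither |
| Thigh, Week 8 | Q4W | none | 4 weeks | neither |
| Thigh, Week 12 | Q4W | Week 13 | 1 week | yes |
| Gluteal, Week 16 | Q4W | Week 17 | 1 week | yes |
| Gluteal, Week 20 | Q4W | none | 4 weeks | neither |
| Gluteal, Screening | Q8W | Week -7 | 1 week | yes |
| Thigh, Day 1 | Q8W | Week 1 | 1 week | yes |
| Thigh, Week 8 | Q8W | Week 9 | 1 week | yes |
| Gluteal, Week 16 | Q8W | Week 17 | 1 week | yes |

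Thigh injections with a 1-week check: Q4W 2/4 = 50%; Q8W 2/2 = 100%.

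**Contact per participant, Day 1 to Week 16.** Q4W: Day 1, Weeks 1, 4, 8, 12, 13, 16 = 7 visits. Q8W: Day 1, Weeks 1, 4, 8, 9, 12, 16 = 7 visits. The totals are equal, but they cover four injections in Q4W and two in Q8W. The imbalance is per injection, not per person.

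**Possible size.** Let q be the share of reactions after the Week 4 and Week 8 injections that the same-day check and the 4-week visit still capture, relative to an injection with a 1-week check. Assume equal true rates across the four injections. Q4W capture relative to full 1-week coverage is

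(1 + q + q + 1)/4 = (2 + 2q)/4

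- q = 1: 4.0/4 = 100%
- q = 0.9: 3.8/4 = 95%
- q = 0.5: 3.0/4 = 75%
- q = 0: 2.0/4 = 50% (limiting case)

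On the same scale Q8W is 100% by definition. That does not mean every Q8W reaction is found: the 1-week window is 3 to 10 days after the dose, so short reactions can be missed there too.

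**Data in a matched table.** With 41 participants per arm and every planned injection given, thigh injection occasions number 41 × 4 = 164 in Q4W and 41 × 2 = 82 in Q8W. Keeping only those with a 1-week visit leaves 41 × 2 = 82 in each arm.

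**The case against.** A reader might infer that the tables do under-count Q4W reactions, or that reactions after the two middle injections go unseen. The documents do not support that. Participants are observed for at least 2 hours after every thigh injection, including those at Weeks 4 and 8. Sites and adverse events are assessed at every visit, so a reaction can be recorded the same day or by history 4 weeks later. Nothing confines ISR counting to the 1-week visits.

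The measurement argument covers a minority of reactions. Section 11.13.1 reports mostly pain, with erythema and induration in a few participants. Pain is graded by functional limitation, which can be recalled, and erythema has symptom-based alternatives at Grades 2 and 3. The phrase on limited duration gives no number of days.

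No ISR contrast is specified, either between arms or between sites. The primary comparison is PK, thigh against gluteal within arm, with no hypothesis test. Raw event counts differ by design anyway (four injections of 2 mL per drug against two of 3 mL). The NRS already provides a matched set for pain at the first and last thigh injections and the Screening and Week 16 gluteal injections.

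The subject-level table is less exposed. Visit totals are equal, the first thigh injection has a 1-week check in both arms, and all 14 injected Phase 1 participants had an ISR after single-dose injections.

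These arguments defeat any claim of demonstrated bias. They do not remove the unequal follow-up per injection. The protocol itself fixes both the visit schedule and the event-level summary, and the tolerability aim in Section 11.13.2 invites the comparisons that this inequality affects.

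**Conclusion.** The schedule difference is a fact: 1-week checks follow 2 of 4 Q4W thigh injections and 2 of 2 in Q8W. The two middle Q4W injections also lack any NRS score. Event-level ISR incidence and severity for Q4W thigh injections may therefore be low relative to Q8W and to the Q4W gluteal Screening injection.

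The size cannot be derived. The values of 95% and 75% illustrate q = 0.9 and q = 0.5 and are not estimates. At q = 1 there is no shortfall, and the protocol does not rule that out. The calculation also assumes equal true rates across injections. The point concerns a descriptive secondary summary and does not touch the PK objective.

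**What to change.** In Section 11.13.8.4.2:

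- Keep the all-injection ISR table as the main safety summary, with a note that ascertainment per injection is unequal.
- Add an event-level ISR table by arm limited to injections with a scheduled 1-week visit. For the thigh these are the first and last injections (Q4W 1 and 4, Q8W 1 and 2), the pairs Table 15 already uses for PK. Take gluteal figures from the Screening and Week 16 injections.
- Show ISRs after the Q4W Week 4 and Week 8 injections separately.
- Base any per-injection comparison between arms, or between thigh and gluteal sites, on the matched table.

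The cost is plan wording and one extra table. No visits are added and no data are dropped. The downside is that the matched table holds half of the planned Q4W thigh injections, which is why it should sit beside the all-injection summary and not replace it.
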